Hypothesis I-a: C-tDCS will be safe in AIS patients receiving EVT with no increased risk of symptomatic intracranial hemorrhage (SICH) within the 24-hour period after EVT. Hypothesis I-b: C-tDCS will not increase the rates of asymptomatic intracranial hemorrhage, early neurological deterioration (NIHSS during the 24-hour period after stimulation), 90-day mortality, and all serious adverse events. Hypothesis I-c: Majority of AIS patients ($\geq 90\%$) will tolerate the C-tDCS by completing at least 75% of the stimulation period with no major stimulation related pain, discomfort and skin changes.

Specific Aim II: To determine the feasibility of delivering C-tDCS as an adjunct and bridge to EVT.

Hypothesis II-a: Adjunctive C-tDCS after endovascular thrombectomy will be started more rapidly after the end of ET procedure over the course of the study and in the last 10 patients, median time from end of ET procedure to C-tDCS initiation will be ≤ 10 minutes. Hypothesis II-b: Bridging C-tDCS prior to endovascular thrombectomy will be started more rapidly over the course of the study and in the last 4 patients, median time from randomization to C-tDCS initiation will be ≤ 10 minutes.

Specific Aim III: To explore the potential imaging and clinical efficacy of tDCS in AIS as an adjunct and bridge to EVT.

1) Early and late penumbral salvage, defined as proportion of penumbral tissue on baseline multimodal MRI that does not proceed to infarct on 2-hour and 24-hour MRI (PWI); 2) Early and late collateral enhancement, evidenced by reduced perfusion lesion volume on 2-hour and 24-hour perfusion-weighted MRI (PWI); 3) Early and late reduction in infarct growth from baseline to 2-hour and 24-hour MRI; 4) Early improvement in neurologic deficit (NIHSS at 24h); 5) Improvement in final 3-month disability and quality of life (modified Rankin scale, AMC Linear Disability Scale, EQ-5D, and Barthel Index)

Impact

This in-hospital safety trial, will identify C-tDCS dose regimens that are feasible, well-tolerated, and preliminarily safe in patients with acute ischemic stroke who undergo ET. Study finding will identify the most promising dose regimens to advance to phase 2b and pivotal phase 3 efficacy trials for three patient populations with pressing need for improved therapies: 1) thrombectomy-eligible patients arriving directly to thrombectomy-capable hospitals who would benefit from post-arrival brain protection; 2) thrombectomy-eligible patients arriving initially

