This proposal is a prospective, single-center, dose-escalation safety, tolerability and feasibility study of C-tDCS as adjunctive and bridging neuroprotection in acute stroke patients undergoing endovascular thrombectomy. Patients with less than a complete EVT reperfusion (the thrombolysis in cerebral infarction (TICI) grading of <2c and 3) will be receiving at least one cycle of adjunct C-tDCS after EVT and at higher dose tiers, one cycle of bridging C-tDCS will be administered before EVT and if EVT results in TICI < 2c/3, then two cycles of adjunct EVT will be applied after EVT. The primary safety endpoints will be symptomatic intracranial hemorrhage during the 24-hour period after thrombectomy. Secondary measures of safety will include asymptomatic intracranial hemorrhage, early neurological deterioration, 3-month mortality and all serious adverse events. Tolerability will be judged based on the percentage of the patients completing the protocol-assigned stimulation treatment and secondarily, the rate and severity of cutaneous, neurologic, nociceptive or

other adverse effects will be assessed. Feasibility endpoints will analyze the speed with which tDCS will be implemented. Finally, we will explore signals of potential efficacy by examining the imaging evidence of infarct growth, and clinical outcomes of early neurologic deficit evolution, and 3-month global disability and health-related quality of life.

D2. Technology

D2.1. tDCS Device and Stimulation Parameters

The study will employ a Soterix™ high-definition DC-Stimulator, owned by the principal investigator. This tDCS unit consists of a stimulator, 4x1 HD interface and an adjustable cap with pre-maid openings that quickly and easily fits different head sizes. (Figure 5). The cap will be loaded with plastic electrode holders. These will be filled with conductance gel (Signa® gel), 1 cm² electrodes will be placed in the holders, and the holder then locked.

D2.2. Montage

The electrode positioning montage will be a 4 to 1-ring configuration, with the center or active electrode connected to cathode and the 4 reference or return electrodes connected to anode. The 4 to 1-ring configuration is chosen to focus the stimulation to the penumbral region. (Fig 6)

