We will implement a traditional 3+3 (rule-based, modified Fibonacci) dose escalation design, with 3:1 randomization to active treatment vs sham control. There will be 6 dose tiers, reflecting increasing intensity and duration of stimulation:

Tier 1 – 1 mA, single 20 - min cycle, will start at the conclusion of the EVT procedure in patients with less than a complete EVT recanalization (the thrombolysis in cerebral infarction (TICI) grading of <2c and 3) and negative immediate post-EVT CT scan for a definitive evidence of intracranial hemorrhage (ICH).

Tier 2 – 2 mA, single 20 min cycle, will start at the conclusion of the EVT procedure in patients with TICI<2c and 3 and negative immediate post-EVT CT scan for a definitive evidence of ICH.

Tier 3 – 1 mA, in 2 treatment cycles. First cycle will be a 20 min cycle, administered after the conclusion of the EVT procedure in patients with TICI<2c and 3 and negative immediate post-EVT CT scan for a definitive evidence of ICH. The second cycle will start 20 minutes after the end of the first cycle, and will last 20 minutes.

Tier 4 – 2 mA, in 2 treatment cycles. First cycle will be a 20 min cycle, administered after the conclusion of the EVT procedure in patients with TICI<2c and 3 and negative immediate post-EVT CT scan for a definitive evidence of ICH. The second cycle will start 20 minutes after the end of the first cycle, and will last 20 minutes.

Tier 5 - 1 mA, in 3 treatment cycles. First cycle will be a 20 min cycle, administered after initial imaging either in the Roland Reagan Medical Center or mobile stroke unit and prior to arterial puncture (cycle will be shorter than 20 minutes if EVT puncture is ready to proceed, in order not to delay EVT). The second cycle will start at the conclusion of the EVT procedure in patients with TICI<2c and 3 and negative immediate post-EVT CT scan for a definitive evidence of ICH (and not sooner than 20 minutes after the end of the first cycle), and will last 20 minutes. The third cycle will start 20 minutes after the end of the second cycle, and will last 20 minutes.

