After randomization and during the stimulation, all patients will be monitored closely by a physician-investigator. NIHSS will be obtained at the end of each 20-minute stimulation cycle and a visual inspection of the skin and rate degree of any potential erythema under the electrode will be performed. Then, a tolerability form will be completed based on validated cutaneous, neurological, and pain items of the PRO-CTAE (Patient-Reported Outcomes version of the Common Terminology Criteria for Adverse Events) (Figure 8).^{40,41}

After the stimulation, nursing neurologic assessments will be performed by Neurointensive Care Unit with extensive experience in monitoring acute stroke patients. Specifically, patients will be monitored for any signs of neurological worsening and will be queried on development of new or worsening neurological symptoms, including headache, dizziness, numbness, or weakness, etc. If any sign or symptom of neurological worsening is suspected, the patient will be immediately assessed by the on-call neurologist and an immediate brain imaging (CT or MRI) will be obtained. Neuro-checks will be performed at 1h and 2h after stimulation and then every 2 hours. Subsequent care will be continued in these settings, including medical management per national guidelines for acute ischemic stroke management issued by the American Stroke Association.⁴² Patients will not receive NSAIDs as concomitant therapy for the first 7 days after enrollment. All patients will undergo a multimodal MRI or CT including standard parenchymal images, non-invasive angiography, and perfusion studies and formal NIHSS assessment at 2-hour and 24-hour following the end of the stimulation tier as part of the study protocol.

D.5. Management pre, during, and post bridging stimulation

At tiers 5 and 6, hospital arriving patients who are candidates for EVT with an LVO detected on CT angiography and are being transferred to agio suite for EVT procedure will receive up-to-20 minutes of stimulation. See section D.4. for care during and post-stimulation.

Figure7: Technician-filled tolerability form	Presence		Severity		Effect on the study treatment (Shortened the stim duration)		Duration/Frequency			Treatment			
	A	P	M	Mod	S	Y	N	< 50 % of stim period	≥50% of stim period	lasted after stim period (min)	None	Con	Med
Adverse Events													
Rash													
Skin dryness													
Hair loss													
Itching													
Hives													

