- Records of all the time metrics related to EVT: time of decision to take to catheter angiography suite for EVT, time of arrival at the catheter angiography suite, time of Groin Puncture, the time that C-tDCS was aborted prior to EVT, door to puncture time, on clot time, time first device deployed, time of first device passed (the times for each pass and deployment will be recorded), Total duration of EVT.
- Type of device uses (stent-retriever vs aspiration catheter)
- Total number of device passes
- NIHSS before and after EVT
- Interval serious adverse events during EVT
- Interval medications/procedures during EVT

D.6.4. Early (2 Hours) After EVT

- NIHSS,
- Multimodal MRI/CT
- Interval serious adverse events
- Interval medications/procedures

D.6.5. Late (24 Hours) After EVT

- NIHSS
- Multimodal MRI/CT
- Interval serious adverse events
- Interval medications/procedures

D.6.6. Day 4

- Modified Rankin Scale (mRS)
- Interval serious adverse events
- Interval medications/procedures

D.6.7. Day 30

- mRS (phone),
- Interval serious adverse events
- Interval medications/procedures

D.6.8. Day 90

- NIHSS,
- Modified Rankin Scale (mRS)
- AMC Linear Disability Scale (granular disability)
- Barthel Index (BI) (activities of daily living)
- EuroQol (EQ-5D) (health-related quality of life)
- Interval serious adverse events
- Interval medications/procedures

D.6.9. Imaging Assessments

- Baseline

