The lead tolerability endpoint is completion of the protocol-assigned stimulation treatment without early cessation due to cutaneous, neurologic, nociceptive or other adverse effects. Experience with tDCS in post-stroke patients indicates only infrequent cutaneous (itching, tingling) adverse effects are likely to occur. Accordingly, for the current study, a patient will be considered to have tolerated the procedure if at least 75% of the stimulus period was completed. The treatment will be considered generally tolerable if, among all enrolled patients, tolerated procedures are achieved in $\geq 90\%$ of patients, assessed with a one-sided p value of 0.025. Secondary tolerability endpoints will be the rate and severity of cutaneous, neurological, and pain items of the technician-filled (Figure 7), descriptively compared between active treatment and sham patients, and between higher and lower dose tiers.

E.3.4. Feasibility Endpoint Analysis (Specific Aim 2)

A time-motion analysis and mock run-throughs will be conducted prior to first enrollment. Nonetheless, it is anticipated that processes to optimize rapid placement of the cap and electrodes will continue to improve with experience gained from initially enrolled patients. The predefined success threshold for feasibility will be median times from randomization to bridging C-tDCS initiation and the time from end of EVT procedure to adjunctive C-tDCS initiation ≤ 10 minutes in the last 4 and 10 enrolled patients, respectively.

E.3.5. Exploratory Efficacy Endpoints Analysis (Specific Aim 3)

E.3.5.1. Exploratory Clinical Efficacy Endpoints

This study is underpowered to definitively determine efficacy, so all clinical efficacy analyses will be purely exploratory and descriptive. Four clinical outcome measures were selected based on their reliability, familiarity to the neurologic community, and adaptability for use in patients who have had a stroke. These endpoints are: the modified Rankin Scale (mRS), a rating of global disability; the Barthel Index (BI), a measure of instrumental activities of daily living; the National Institutes of Health Stroke Scale (NIHSS), a measure of neurologic deficit severity; and the EuroQol (EQ-5D), an assessment of health-related quality of life; and AMC Linear Disability Scale, a granular degree of disability.

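### The bridging feasibility rule does not say how to score a patient whose puncture is ready before stimulation starts, and it takes no account of the minutes delivered

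*Combined protocol and SAP*

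**What the plan says.** Specific Aim II in section A is about whether C-tDCS can be delivered as an adjunct and a bridge to EVT. Hypothesis II-b makes this concrete for bridging as "median time from randomization to C-tDCS initiation will be ≤ 10 minutes". E.3.4 repeats the 10-minute limit as the predefined success threshold, "median times from randomization to bridging C-tDCS initiation and the time from end of EVT procedure to adjunctive C-tDCS initiation ≤ 10 minutes", applied "in the last 4 and 10 enrolled patients, respectively" (4 for bridging, 10 for adjunctive stimulation). D.1 describes the scope in the same way: "Feasibility endpoints will analyze the speed with which tDCS will be implemented".

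For Tiers 5 and 6, section D.4 (Dose Tiers and Randomization) says of the bridging cycle: "cycle will be shorter than 20 minutes if EVT puncture is ready to proceed, in order not to delay EVT". D.5 says that patients "will receive up-to-20 minutes of stimulation". No minimum is stated in either place. Among the EVT time metrics, D.6.4 collects "the time that C-tDCS was aborted prior to EVT", but no feasibility criterion uses it.

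Two other provisions bear on the point. E.2.1 says that missing data will be handled by multiple imputation, with complete-case and worst-outcome sensitivity analyses. E.3.3 says, for tolerability, that "a patient will be considered to have tolerated the procedure if at least 75% of the stimulus period was completed".

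**The concern.** Start of stimulation and readiness for puncture are competing events. If puncture is ready first, the patient has no start time, and the cause is often that set-up was slow relative to the angiography team. The missing value therefore carries information: it tends to belong to the patients for whom bridging was least feasible. The plan's own tools handle this badly. Imputation supplies a time for something that did not occur, and a complete-case analysis removes the unfavourable patients. The worst-outcome analysis would treat them sensibly, but E.2.1 makes it only a sensitivity analysis.

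Separately, a start at 9 minutes counts the same whether 1 minute or 20 minutes of stimulation follows. Aim II concerns delivery, and Tiers 5 and 6 differ from Tiers 3 and 4 essentially by the added bridging cycle. At stake is how far a statement that bridging is feasible can be relied on when regimens are chosen for later trials.

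**Working it through.** **Plan figures.** The sample size reproduces: 6 tiers × (3 + 1) = 24, and 6 × (6 + 2) = 48. Tiers 5 and 6 therefore supply 2 × 4 = 8 to 2 × 8 = 16 patients, of whom 6 to 12 are active. The 10-minute limit is a chosen cut-off with no error rate attached, so there is nothing to reproduce.

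**Minutes delivered.** Let S be the start of stimulation and P the time when puncture is ready, both in minutes after randomization. Delivered bridging time is D = min(20, max(0, P − S)). The documents give no value for P, so it is varied here with S = 10, the latest start within the limit:

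| P (min) | 11 | 15 | 20 | 25 | 30 |
|---|---|---|---|---|---|
| D (min of 20) | 1 | 5 | 10 | 15 | 20 |

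As a limiting case, four starts at 9 minutes with puncture ready at 10 give a median of 9. The rule is met with 1 of 20 minutes delivered in each patient.

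**Scoring never-starters.** The median of four values is the mean of the 2nd and 3rd in order. Suppose that every patient who starts does so at 8 minutes:

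| Never started (of 4) | Never-starters dropped | Never-starters ranked as late |
|---|---|---|
| 0 | 8, met | 8, met |
| 1 | 8, met | 8, met |
| 2 | 8, met | beyond 10, not met |
| 3 | 8, met | beyond 10, not met |

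**The tolerability rule as a check.** If the stimulus period is read as three 20-minute cycles and both adjunctive cycles are complete, the fraction completed is (b + 40)/60 for b bridging minutes. For b = 5 it is 45/60 = 75%, which counts as tolerated. For b = 1 it is 41/60 = 68.3%, which does not. If the period is instead read as the shortened cycle allowed by D.5, any duration counts as complete.

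**Size.** Assumptions: S is lognormal with log-SD 0.5, P is lognormal with log-SD 0.4, the two are independent, and stimulation starts only if S < P. There were 200,000 simulated sets of four patients. The table gives the percentage of sets in which the median is at most 10 minutes.

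| Median S / median P (min) | Never-starters dropped | Never-starters ranked as late |
|---|---|---|
| 12 / 15 | 52% | 19% |
| 10 / 20 | 61% | 45% |
| 8 / 30 | 79% | 77% |

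At 12/15, 64% of patients start. Median bridging delivered is about 2.9 minutes when never-starters count as zero, and 6.7 minutes among starters. At 10/20, among the sets that meet the rule with never-starters dropped, the median delivered is under 15 minutes in 82%, under 5 minutes in 12% and under 2 minutes in 3%. With median readiness of 30 to 40 minutes and median start of 8 to 12, the two scorings differ by at most about 6 percentage points and the median delivered is 17 to 20 minutes. At 40 minutes the gap is no more than about 3 points.

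**The case against.** A reader might infer that the plan judges bridging only among patients who start. The text does not say so: E.3.4 refers to enrolled patients. What is missing is a rule for those who never start. E.2.1 does offer a worst-outcome sensitivity analysis that comes close to the right scoring. It is generic, does not mention feasibility and is secondary to imputation, so the gap remains.

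A reader might also infer that bridging could be taken forward with almost no stimulation given. The limiting case shows that the start-time rule alone permits this, but the documents do not make that rule a stand-alone gate. D.6.10.2 rests the decision on further development on an assessment of all outcome measures, and abort times will be on record. D.1 openly defines feasibility as speed. The 75% tolerability rule also screens some of the extreme cases. That check is partial: its lead endpoint concerns stopping for adverse effects, it can pass 5 of 20 bridging minutes, and it does not enter the feasibility decision.

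The simulation depends on readiness times that nobody has stated. Section B cites a 60–120 minute window from door to recanalization, and bridging may begin in a mobile stroke unit, so long lead times are plausible. The simulation also treats all four patients alike, whereas 3:1 allocation would give about three active and one sham, and the plan does not say whether sham starts count. These objections limit the size of the point. They do not supply the missing rule.

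**Conclusion.** The point holds as a gap in the success rule. E.3.4 leaves the score of a never-started patient open, the stated default would impute a start that did not occur, and dropping such patients allows the rule to be met with 3 of 4 never started. These statements follow from the text and simple arithmetic. The minutes delivered, which Aim II needs for interpretation, are recorded but not used.

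The practical size is uncertain. It runs from a large difference (52% v 19%) if puncture is typically ready soon after set-up, to almost none if readiness takes 40 minutes or more. The documents do not support saying that the plan excludes never-starters, or that the trial would recommend regimens that were never really given. Nor do they support carrying the 75% fraction over as a success threshold for delivery. It was set for tolerability, and a bar that rewards longer stimulation before puncture could pull against the aim of not delaying EVT.

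**What to change.** In E.3.4, state that the bridging median is taken over all of the last 4 patients assigned to bridging, and that anyone not started before puncture is ranked as later than 10 minutes, neither imputed nor excluded. With two or more such patients the criterion is then not met. State also whether sham starts count among the four.

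Report beside the median the proportion of assigned patients who started and the bridging minutes delivered per patient. The start time is already needed for the existing endpoint, and the abort time is collected under D.6.4. Add no minimum-duration success threshold, and leave the rule that protects EVT timing unchanged.

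The cost is two or three sentences and no new data. The downside is a slightly harder feasibility bar: one never-starter among four can still pass, two cannot.

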Tier 6 - 2 mA, in 3 treatment cycles. First cycle will be a 20 min cycle, administered after initial imaging either in the Roland Reagan Medical Center or mobile stroke unit and prior to arterial puncture (cycle will be shorter than 20 minutes if EVT puncture is ready to proceed, in order not to delay EVT). The second cycle will start at the conclusion of the EVT procedure in patients with TICI<2c and 3 and negative immediate post-EVT CT scan for a definitive evidence of ICH (and not sooner than 20 minutes after the end of the first cycle), and will last 20 minutes. The third cycle will start 20 minutes after the end of the second cycle, and will last 20 minutes.

Patients in the sham stimulation arm at all the tiers will have the cap and electrodes in place, but without any delivered electrical stimulation. While the highest dose tier in this study is expected to be fully safe, based on preclinical and clinical studies ^{11,18}, since this is a first-in-human study in acute stroke, a formal escalation to higher dose tiers is prudent.

[figure not shown]

Figure 7. This figure shows the 6 escalating tiers. Blue represents 1 mA, purple shows 2 mA of C-tDCS. The black/white neuroangi suite icon represents the endovascular thrombectomy (EVT) procedure, occurring before the adjunctive C-tDCS at all tiers if EVT results in a less than a complete recanalization (TICI <2c, 3). At tiers 5 and 6, bridging C-tDCS occurs for up to 20' before EVT. Symptomatic ICH (SICH) in none of the three C-tDCS patients in a tier will result in escalation. However, if SICH occurs in one C-tDCS patient, 3 more C-tDCS patients and 1 more sham will be enrolled at the same tier.

D.4. Management pre, during, and post adjunctive stimulation period

As soon as the endovascular thrombectomy (EVT) ends, a CT head will be obtained in patients with less than a complete EVT reperfusion (TICI < 2c,3) and if negative for definitive evidence of intracranial hemorrhage, then the patient will be randomized, and the adjunct stimulation will be initiated in neurosurgical intensive care unit according to the tier that patient is assigned to.

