The study sample size derives from the use of the 3+3, rule-based, modified Fibonacci, dose escalation design, with 3:1 randomization to active treatment vs sham control. There will be 6 dose tiers, reflecting increasing intensity and duration of stimulation (Figure 7). The 3+3 study design (3 patients and 1 sham) with 6 dose tiers yields a sample size of at least 24 and potentially up to 48. The 3+3 design is the classical approach to dose escalation in first-in-human studies.^{47,48} While newer, adaptive designs for dose escalation trials have been developed, they are more complex and have limited advantages when major toxicities are not expected.⁴⁹ Therefore, the rule-based, 3+3 design remains the dominantly employed approach in current dose-escalation studies. We will take every step to avoid missing data by scheduling of the follow-up visits early in visit time windows and readiness to travel to the patient's location to perform needed assessments. Should any missing data occur, primary analyses will be performed using multiple imputation, with sensitivity analyses including complete case and worst possible outcome analyses.⁵⁰

E.2.2. Baseline characteristics

The demographic and baseline clinical characteristics of the study population will be delineated with standard descriptive statistics. Categorical variables describing the clinical history, examination findings, and initial treatment will be summarized by frequencies. Continuous variables such as vital signs, laboratory results, and time variables will be characterized by means, standard deviations, and 95% confidence intervals (CI). Ordinal and non-normally distributed variables (such as the NIHSS) will be characterized by medians and interquartile ranges. Baseline characteristics will be compared between the tDCS stimulation group with sham group to assess covariate balance. Wilcoxon Rank-Sum tests will be used for continuous or ordinal variables; Fisher's exact tests and chi-square tests will be used for grouped or nominal categorical variables.

E.2.3. Safety and Tolerability (Specific Aim 1)

E.2.3.1 Dose Escalation

The study Data and Safety Monitoring Board (DSMB) will meet at the completion of each dose tier, review all safety data, and determine whether the study will proceed to the next dose tier. DSMB deliberations will be

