guided by: 1) a formal stopping/escalation rule, based on the occurrence of the lead safety endpoint, symptomatic intracranial hemorrhage (SICH), and 2) The DSMB members' clinical judgement upon review of all other safety outcomes. The formal dose escalation rule uses SICH frequency to gate the occurrence and pace of escalation through the 6 dose tiers. If no SICH occurs in the 3 active patients at a dose tier, enrollment may escalate to the next dose tier. If one SICH occurs, 3 more active (and 1 more control) patient will be enrolled at that dose tier before escalation. If 2 SICHs occur at a dose tier, further study enrollment is held until detailed review by the DSMB (Fig 6). In addition, whenever the formal SICH criteria for dose escalation has been met, the DSMB will formally meet, review the SICH data and all other safety data, and advice regarding proceeding to the next tier, continuing at the current tier, or placing the study on hold.

E.2.3.2. Primary Safety Endpoint Analysis

For the final statistical analysis of the primary SICH safety endpoint, a chi-square test will be used to detect differences in the rate of SICH between the active treatment and sham patients and higher and lower dose tiers. The treatment will be considered to have exhibited adequate safety in the current trial to proceed to future, larger, pivotal efficacy trials if tDCS results in lower or equivalent rates of SICH compared to sham.

E.2.3.3. Secondary Safety Endpoints Analysis

In secondary safety endpoint analyses, the following will be compared between the active treatment and sham patients, and between higher and lower dose tiers, using chi-squared tests: **1)** Asymptomatic ICH by 24h (intracranial hemorrhage not associated with NIHSS worsening ≥ 4); **2)** Early neurologic deterioration (worsening ≥ 4 on NIHSS during the 24-hour period after stimulation, with or without intracranial hemorrhage); **3)** All-cause mortality at day 90 (mRS); and **4)** All serious adverse events.

E.3.3. Tolerability Endpoint Analysis

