Clinical efficacy endpoints will be characterized in the active and sham patients, and in higher and lower dose tiers. Early course clinical efficacy endpoints of greatest interest that will be explored are: **1)** Normalized change in neurologic deficit from baseline to 24h (normalized delta NIHSS – linear variable, analyzed with means and 95% CIs; and **2)** Degree of neurologic deficit at 24h (NIHSS – quasi-linear variable, analyzed with means and 95% CIs). Final outcome clinical efficacy endpoints of greatest interest that will be explored are: **1)** Degree of disability at 90 days, assessed across all 7 levels of the modified Rankin Scale – ordinal variable, analyzed with medians (IQRs) and means (95% CIs); **2)** Functional independence (mRS 0-2) at 90 days – binary variable, analyzed with rates and 95% CIs; **3)** Granular degree of disability at 90 days (AMC Linear Disability Scale) –

linear variable, analyzed with means and 95% CIs; and **4) Health-related quality of life (EQ-5D)** – linear variable, analyzed with means and 95% CIs.

E.3.5.2. Exploratory Imaging Biomarker Efficacy Endpoints

This study is underpowered to definitively determine efficacy, so all imaging efficacy analyses will be purely exploratory and descriptive. The imaging efficacy analysis will be done on the subgroup of patients (including tier 5 and 6 patients who have presence of salvageable penumbra in their entry criteria) with baseline pre-EVT penumbral imaging demonstrating presence of salvageable penumbra with $T_{max} > 6$ sec/ ischemic core volume of ≥ 1.2 .

Imaging biomarker efficacy endpoints will be characterized in the active and sham patients, and in higher and lower dose tiers, using means and 95% confidence intervals. The six imaging efficacy endpoints of greatest interest that will be explored are: early and late penumbral salvage, early and late collateral flow enhancement, and early and late infarct growth.

References:

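### The 24-hour NIHSS and 90-day scales are summarised by arm without baseline adjustment, although baseline NIHSS is collected; with 6 to 12 sham patients this adds avoidable noise

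*Combined protocol and SAP*

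**What the plan says.** The allocation in E.2.1 is "with 3:1 randomization to active treatment vs sham control". The same section gives the tier make-up and total as "3 patients and 1 sham) with 6 dose tiers yields a sample size of at least 24 and potentially up to 48". E.2.3.1 adds to both arms when a tier expands: "If one SICH occurs, 3 more active (and 1 more control) patient will be enrolled at that dose tier before escalation".

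For clinical efficacy, E.3.5.1 states: "Clinical efficacy endpoints will be characterized in the active and sham patients, and in higher and lower dose tiers". It lists means with 95% CIs, medians with IQRs, or rates with 95% CIs. For imaging, E.3.5.2 plans the same kind of summary, means with CIs: "Imaging biomarker efficacy endpoints will be characterized in the active and sham patients, and in higher and lower dose tiers, using means and 95% confidence". Neither section names a regression, a covariate or a stratified estimate. Both call the study underpowered for efficacy and the analyses exploratory and descriptive.

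Baseline does enter some endpoints. One is "Normalized change in neurologic deficit from baseline to 24h" (E.3.5.1). The six imaging measures in D.6.9 are differences from baseline volumes or are defined on baseline penumbra. The 24h NIHSS, mRS, functional independence, AMC scale and EQ-5D use no baseline value.

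Baseline NIHSS is in the Schedule of Events (D.6.1) and in D.6.2. The thrombectomy record (D.6.4) also lists "NIHSS before and after EVT". E.2.2 plans a comparison of baseline characteristics between arms but attaches no consequence to an imbalance.

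**The concern.** A sham arm this small will often differ from the active arm at baseline by chance. Where the baseline value predicts the outcome, part of any raw difference in 24h NIHSS or 90-day disability is then a difference in starting severity. The plan would show the imbalance through E.2.2 but has no prespecified estimate that allows for it. Adjustment would then be chosen after the imbalance had been seen.

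No efficacy decision rule is at stake. However, the Impact paragraph expects the findings to point to regimens for later trials, and D.6.10.2 says the next step will weigh all the outcome measures. The efficacy summaries will be read for a signal, so precision that can be had at no cost is worth taking.

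**Working it through.** **Sample size.** 6 x (3 + 1) = 24 and 6 x (6 + 2) = 48, which reproduces the plan's 24 to 48. Completed enrolment therefore runs from 18 v 6 to 36 v 12. The documents give no efficacy SD, effect size, alpha or power, so everything below is in SD units.

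**Chance imbalance.** The SE of the baseline mean difference is sqrt(1/n_active + 1/n_sham).
- 18 v 6: sqrt(1/18 + 1/6) = 0.471; P(|difference| > 0.5 SD) = 2 x [1 - Phi(0.5/0.471)] = 28.9%.
- 36 v 12: sqrt(1/36 + 1/12) = 0.333; 2 x [1 - Phi(1.5)] = 13.4%.

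**Effect on the raw difference.** With baseline-outcome correlation r (assumed 0.3, 0.5 or 0.7), a 0.5 SD imbalance shifts the raw arm difference by 0.5r, that is 0.15, 0.25 or 0.35 SD. Over repeated trials, baseline accounts for r² of the variance of the raw difference: 9%, 25% or 49%.

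**Noise or bias.** In simulation under no effect (20,000 replicates per setting; 18 v 6, 36 v 12 and 6 v 2) the unadjusted comparison rejected 4.8% to 5.1% of the time at a nominal 5%. The randomised contrast is therefore noisy but valid.

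**Gain from adjustment.** With one covariate, adjusted SE = raw SE x sqrt[(1 - r²)(1 + 1/(N - 4))], with the t quantile on N - 3 rather than N - 2 degrees of freedom. The 95% CI half-widths for the arm difference are:

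| Active v sham | Unadjusted | r = 0.3 | r = 0.5 | r = 0.7 |
|---|---|---|---|---|
| 18 v 6 | 0.98 | 0.96 | 0.87 | 0.72 |
| 36 v 12 | 0.67 | 0.65 | 0.59 | 0.48 |
| 12 v 4 (tiers 5-6, both expanded) | 1.24 | 1.24 | 1.12 | 0.93 |
| 6 v 2 (tiers 5-6, minimum) | 2.00 | 2.24 | 2.03 | 1.68 |

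At 18 v 6 the interval narrows by about 2%, 11% and 27%.

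A tier-group term costs one more degree of freedom. Because allocation is 3:1 in every tier, that term is orthogonal to arm. The SE factor becomes sqrt[(1 - r²)(1 + 1/19)], with t on 20 df (2.086) against 22 df (2.074). The narrowing is then about 2%, 11% and 26%.

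**Change scores are not a substitute.** With equal variances, a plain change score has SE = raw SE x sqrt[2(1 - r)]. At 18 v 6 this is 0.558, 0.471 and 0.365 for r = 0.3, 0.5 and 0.7, against 0.461, 0.418 and 0.345 after adjustment. At r = 0.3 the change score is less precise than the raw mean; at r = 0.5 it gains nothing. Normalized delta NIHSS is not a plain change score, so these figures are only illustrative.

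**Imaging subset.** The penumbral substudy criteria in D.3.1 require a tier with a bridging session, which means tiers 5-6. E.3.5.2 describes its subgroup as including those tiers, so its extent is not fully clear. If it is tiers 5-6 only, a 1-4 v 5-6 term is constant and cannot be estimated. At 6 v 2, adjustment widens the interval by about 12% at r = 0.3 and 2% at r = 0.5, and narrows it by 16% only at r = 0.7.

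**Timing of the covariate.** For adjunctive stimulation, D.4 (management section) describes the end of EVT, then CT, and "if negative for definitive evidence of intracranial hemorrhage, then the patient will be randomized". At tiers 1-4 a post-EVT NIHSS would therefore be the better covariate, provided it is recorded before randomisation. D.6.4 lists an NIHSS after EVT but does not place it relative to randomisation.

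**The case against.** The strongest reply is that the plan already treats efficacy as underpowered and descriptive. It sets no efficacy test or threshold, and its stated criterion for proceeding (E.2.3.2) rests on SICH. It also plans a balance check. All of this stands, and it is why the point is minor. It does not remove the case for prespecifying a more precise descriptive estimate from a value already in hand.

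Three stronger readings are tempting, and the documents do not support them.
- A reader might infer that chance imbalance drives or biases the result. At the assumed correlations it accounts for 9% to 49% of the variance of the raw difference. The rest is small-sample noise that adjustment leaves, and the randomised contrast keeps its nominal error rate.
- A reader might infer that the plan ignores baseline, or that there are only six shams. Normalized delta NIHSS and all six imaging endpoints use baseline, and expansion can take the sham arm to 12.
- A reader might infer that, at tiers 1-4, the last NIHSS before randomisation is collected but unused, and that delta NIHSS therefore carries EVT-driven change from before randomisation. The schedule lists Baseline separately from the assessments around EVT, which makes this plausible. However, the plan does not define the baseline in delta NIHSS or say that the post-EVT score precedes randomisation.

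It is also fair to say that an adjusted active v sham difference does not choose between dose tiers. The higher v lower tier comparison is filled in sequence, not randomised, so the statement about noise without bias does not extend to it. The proposed model does not repair it.

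**Conclusion.** The point holds as a minor one. The 24h NIHSS and 90-day scales are planned as unadjusted summaries by arm while baseline NIHSS is available. The chance of a baseline imbalance above 0.5 SD is 29% at minimum enrolment and 13% at maximum.

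Adjustment would narrow the active v sham CI at 18 v 6 by between 2% and 27% over assumed correlations of 0.3 to 0.7. At the low end the gain is negligible. These figures assume that all six tiers complete, 3:1 allocation in each tier, a linear relation with common variance, and correlations that the documents do not supply. The conclusion covers the clinical outcomes in the full cohort, not an imaging subset with about 2 to 4 shams.

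**What to change.** Add to E.3.5.1, for 24h NIHSS, the AMC Linear Disability Scale and EQ-5D, an exploratory linear model on arm, baseline NIHSS and tier group (1-4 v 5-6). Report the adjusted active-sham difference with its 95% CI. Keep the planned raw summaries, including those for mRS and functional independence.

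State which NIHSS is the covariate. At tiers 1-4, use the post-EVT score if it is recorded before randomisation; otherwise use the baseline score. At tiers 5-6, use the baseline score. If the two are mixed, say that a common slope is assumed. Say also which assessment is the baseline in normalized delta NIHSS.

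State whether the imaging subset is limited to tiers 5-6. If it is, leave the imaging endpoints as unadjusted summaries.

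This is a free improvement. It needs SAP wording only, with no added patients or visits, and baseline NIHSS is already collected. The post-EVT option depends on confirming the timing of that score.
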